4.7.2 Reporting of serious adverse events

When the investigator(s) becomes aware of an SAE during the course of the study, the SAE must be reported to the local monitor or other AstraZeneca representative within one (1) day (ie, immediately but no later than the end of the next business day).

All SAEs have to be reported, whether or not considered causally related to the investigational product. All SAEs will be recorded in the case report form. The principal investigator is responsible for informing the Institutional Review Board (IRB) **in the US** and the IRB through the head of the study center **in Japan**, and/or the Regulatory Authority of the SAE as per local requirements.

The AstraZeneca representative will work with the investigator(s) to compile all the necessary information to ensure that the appropriate AstraZeneca Drug Safety Department receives a report within one day for all fatal and life-threatening cases.

In Japan, the AstraZeneca representative will inform the AstraZeneca Drug Safety Department (Japan) of it by day one, and will work with the investigator(s) to compile all the necessary information and ensure that the AstraZeneca Drug Safety Department (Japan) receives a report within 4 calendar days.

In the US, the AstraZeneca representative will inform the AstraZeneca Drug Safety Department (US) of it within five calendar days.

If a non-serious AE becomes serious, this and other relevant follow-up information must also be provided to AstraZeneca within 1 day as described above.

The following procedure must be followed in the case of a serious adverse event. The same contact information is to be used in case of medical emergency.

YOU MUST REPORT ANY SERIOUS ADVERSE EVENT, INCLUDING DEATH DUE TO ANY CAUSE, IMMEDIATELY. COMPLETE THE ASTRAZENECA SERIOUS ADVERSE EVENT REPORT FORM AND CONTACT ONE OF THE PEOPLE LISTED IN THE ASTRAZENECA EMERGENCY CONTACT PROCEDURE ON PAGE 2 OF THIS PROTOCOL.

YOU MUST FOLLOW ALL SUBJECTS WITH A SERIOUS ADVERSE EVENT, INCLUDING DISCONTINUED SUBJECTS, UNTIL RESOLUTION OF THE ADVERSE EVENT.

5. STUDY MANAGEMENT

5.1 Monitoring

5.1.1 Study monitoring

The monitoring of this study will be performed in accordance with the principles of Good Clinical Practice (GCP) as laid out in the International Conference on Harmonisation (ICH) document “Good Clinical Practice: Consolidated Guideline”.

In Japan, the monitoring of this study will also be performed in accordance with Japanese GCP (Ministry of Health and Welfare Ordinance No. 28, 27 March 1997).

5.1.2 Data verification

It is a prerequisite of this study that the study monitor has direct access to source data for data verification. This will be done by comparing data from the CRFs with those in the subject’s medical notes (permission from the subject will be sought as part of the consent process). Such verification is an essential element of quality control, as it allows the rectification of transcription errors and omissions.

There is no data for which the CRFs will act as the source data for the purpose of this study.

Monitoring will routinely be performed prior to the transfer of data to Data Management.

5.1.3 Direct access to source data

The monitor(s) will verify data from the CRFs against source data before collecting the CRFs to ensure accuracy and completeness of documentation, and assure that the principal investigator has submitted the CRFs to AstraZeneca. For any change or amendment in the collected CRFs, the monitor will assure that the principal investigator has reported to the sponsor the change (or amendment), date, and the reason in a written form.

In Japan, the head of the study center and the investigator(s) should cooperate for monitoring and audit by AstraZeneca, and accept inspection by the IRB or regulatory authorities. All study documents such as raw data should be open for direct access to source data at the request of the monitor and the auditor of AstraZeneca, the IRB, or regulatory authorities.

5.2 Archiving of study documentation

AstraZeneca will retain all documentation pertaining to this study in AstraZeneca in Japan and the US for as long as AZD6140 is available for human consumption.

In Japan, the head of the study center will retain all documentation pertaining to this study for the longer period of either at least 15 years after study completion or the designated period in GCP. The records should be managed by a responsible person appointed by the head of the study centre. However this is not always applied to those that are not preservable such as blood samples.

In the US, The principal investigator will retain all documentation pertaining to this study for the longer period of either at least 15 years after study completion or the designated period in GCP.

5.3 Audits and inspections

Authorised representatives of AstraZeneca, a regulatory authority, an IRB may visit the center to perform audits or inspections, including source data verification. The purpose of an AstraZeneca audit or inspection is to systematically and independently examine all study related activities and documents to determine whether these activities were conducted, and data were recorded, analysed, and accurately reported according to the protocol, GCP guidelines of the ICH and any applicable regulatory requirements. The investigator(s) should contact AstraZeneca immediately if contacted by a regulatory agency about an inspection at his or her center.

5.4 Training of staff

The principal investigator will maintain a record of all individuals involved in the study (medical, nursing and other staff). He or she will ensure that appropriate training relevant to the study is given to all of these study staff, and that any new information of relevance to the performance of this study is forwarded to the study staff involved.

5.5 Changes to the protocol

Study procedures will not be changed without the mutual agreement of the principal investigator and AstraZeneca.

If it is necessary for the study protocol to be amended, the amendment of the study protocol must be notified to or approved by each IRB, and, if applicable, also the local regulatory authority, before implementation. Local requirements must be followed. It is also possible to create a new version of the study protocol (Amended protocol) if needed in that case.

If a protocol amendment requires a change to a particular center's Written Informed Consent Form, then AstraZeneca and the center's IRB must be notified. Approval of the revised Written Informed Consent Form by AstraZeneca and by the IRB is required before the revised form is used.

AstraZeneca will distribute amendments (and new versions of the protocol, Amended Protocol, if needed) to each principal investigator who in turn is responsible for the distribution of these documents to the IRB, and to the study staff at his or her center. The distribution of these documents to the regulatory authority will be handled according to local practice.

5.6 Study agreements

The principal investigator at each center must comply with all the terms, conditions, and obligations of the clinical study agreement for this study. In the event of any inconsistency between this protocol and the study agreement, this protocol shall prevail.

5.7 Study timetable and termination

The study is expected to start on _____ and to be completed by _____

Discontinuation or suspension of the whole study program

AstraZeneca will examine appropriateness of continuation of the study when the following situation occurs:

- When AstraZeneca obtains the information related to the quality, efficacy and safety of the investigational product and other important information for adequate conduct of the study.
- When the protocol requires changes and the study center cannot comply with the changed protocol.
- When AstraZeneca cannot approve the request of an amendment in the protocol from the head of the study center according to the opinions of the IRB.
- When the IRB determines that the study should not be continued and subsequently the head of the study center instructs the discontinuation of the study.
- When the study center violates significantly or continuously the GCP, the protocol or study contract.
- When any of the stopping criteria for dose escalation (see Section 3.1.1) are met and the dose escalation is decided to be stopped.

If AstraZeneca decides to withdraw or suspend the study, the investigator(s), the head of the study center and regulatory authorities should be informed of the fact in a written form clarifying the reason.

The investigator(s) will immediately notify the decision to the subjects, give appropriate medical treatment, take necessary measures, and record treatment or measures provided on the source documents.

Completion of the study

Upon terminating the study, the investigator(s) will report in writing the completion of the study as well as a summary of the results to the head of the study center in accordance with the study center's rules. The head of the study center will then notify, in writing, the IRB and AstraZeneca and will also provide a summary of the results to both parties.

5.8 Data management

5.8.1 Case report forms

CRFs will be provided for the recording of data. The CRFs will be printed on four-part carbonless paper. Data should be recorded directly and legibly from the source documents

onto the CRFs, preferably in black ballpoint pen. Corrections to the CRFs should be made legibly, initialled and dated. Correction fluid or covering labels must not be used. The top original (white) and the first (yellow) and second (green) copies of each completed CRF will be collected and returned to the AstraZeneca designee; the investigator(s) will retain the third copy (manila).

The AstraZeneca Monitor will check data at the monitoring visits to the study center. The principal investigator, together with the AstraZeneca Monitor, will ensure that the data in the CRFs are accurate, complete and legible.

AstraZeneca Data Management will enter the CRF data on an ongoing basis into their standard commercial database. The data will be verified and reviewed with electronic edit checks comprised of validated computer programs and manual data review. Any missing, inconsistent or illegible entries into the CRFs will be referred back to the investigator(s) via the site monitor using Data Query Forms. Responses should be received by Data Management and updated within an agreed number of days upon generating the data queries. Clean file will be declared when all of the following have been completed: all data have been accounted for and have been databased; all edit checks have been run and data discrepancies have been resolved or accepted; all serious adverse events have been reconciled with the clinical database; all coding is complete and has been medically reviewed and approved; and quality control of the database against the CRFs and relevant data sources has been completed.

6. STATISTICAL METHODS AND DETERMINATION OF SAMPLE SIZE

6.1 Statistical evaluation

A comprehensive Statistical Analysis Plan (SAP) will be prepared and finalized before database lock.

6.2 Description of outcome variables in relation to hypotheses

6.2.1 Safety and Tolerability

Incidence and severity of adverse events, 12-lead ECG, blood pressure/pulse rate, body temperature, laboratory parameters (haematology, clinical chemistry, urinalysis, haemocult for Japanese subjects) and physical examination.

6.2.2 Pharmacokinetics

Plasma concentrations of AZD6140 and its metabolite AR-C124910XX will be listed and depicted graphically as a function of time relative to the first dose (Day 1) after single dose and relative to Day 10 morning dose for all subjects receiving AZD6140. Following single dose administration on Day 1 pharmacokinetic parameters C_{max} , t_{max} , $t_{1/2}$, AUC_{0-12} , AUC_{0-t} and AUC for AZD6140 and AR-C124910XX and AZD6140 CL/F (apparent oral clearance) and V_z/F (terminal phase volume of distribution) will be estimated by non-compartmental analysis. Following multiple dosing, on Day 10 pharmacokinetic parameters $C_{ss,max}$, $C_{ss,min}$, $C_{ss,av}$, t_{max} , $t_{1/2}$ and $AUC_{ss,\tau}$ for AZD6140 and AR-C124910XX and, AZD6140 steady state CL_{ss}/F will be estimated by non-compartmental analysis.

AZD6140 and AR-C124910XX C_{max} and $C_{ss,max}$ will be estimated as the highest measured concentration after Day 1 single oral dose and in a 12-hour dosing interval on Day 10 at steady-state, respectively. Correspondingly, t_{max} will be the time to maximum concentration following a single oral dose or within a dosing interval at steady state. $C_{ss,min}$ will be the concentration at the end of a dosing interval at steady state. AZD6140 and AR-C124910XX $C_{ss,av}$, the average concentration in a dosing interval at steady state will be estimated as the ratio of $AUC_{ss,\tau}$ and dosing interval. The terminal elimination rate constant (λ_z) will be calculated by log-linear regression of the terminal portion of the concentration-time profile. The terminal elimination half-life ($t_{1/2}$) will be calculated as $0.693/\lambda_z$. AUC following single oral dose will be calculated using the linear trapezoidal method up to the last measurable concentration (AUC_{0-t}) and thereafter by extrapolation of the terminal elimination phase to infinity. $AUC_{ss,\tau}$ will be calculated using the linear trapezoidal method over the 12 hour dosing interval at steady state. AZD6140 CL/F and CL_{ss}/F will be estimated as the ratio of AZD6140 dose and AUC following the single oral dose and as the ratio of AZD6140 dose and Day 10 $AUC_{ss,\tau}$ at steady state, respectively. The terminal phase volume of distribution, V_z/F , of AZD6140 will be estimated as the ratio of AZD6140 CL/F to λ_z . Accumulation ratio of AZD6140 and AR-C124910XX will be estimated as a ratio of Day 10 $AUC_{ss,\tau}$ to Day 1 AUC_{0-12} .

6.2.3 Pharmacodynamics

6.2.3.1 ADP-induced inhibition of platelet aggregation

Percentage inhibition, %PAI, from pre-dose baseline will be calculated at each time post-dose using the following formula for ADP-induced aggregation:

$$\%PAI = 100 \times \frac{(PA_{BL} - PA_T)}{PA_{BL}}$$

where PA_T is the response at time 'T', and PA_{BL} is the response at pre-dose baseline on Day 1. Percentage inhibition will be restricted to the closed interval [0,100]; any data falling outside this range will be truncated to the appropriate limit.

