4.3 Pharmacodynamic measurements

4.3.1 ADP-induced platelet aggregation

Two 4.5 mL blood samples will be collected into *siliconized glass Vacutainer*[®] tubes which contain 0.5 mL of 0.105M (equivalent to 3.2%) buffered citrate solution. These samples will be used to measure inhibition of platelet aggregation by optical aggregometry, using 20 μ mol ADP as the agonist and run in duplicate, at the defined time points (See [Table 7](#)) at Visit 2.

Final and maximum extent of aggregation will be recorded. Final extent of aggregation will be measured at a point where the curve has been constant for at least 1 minute. The date and time of collection will be recorded on the appropriate CRF. Details of the methods used will be agreed upon in writing by the sponsor and the principal investigator prior to the start of the study.

%PAI from pre-dose on Day 1 will be calculated at each time using the following formula for:

$$\%PAI = 100 \times \frac{(PA_{BL} - PA_T)}{PA_{BL}}$$

- where PA_T is the mean response at time ‘T’, and PA_{BL} is the mean response at pre-dose on Day 1. Percentage inhibition will be restricted to limits 0 and 100. Any data falling outside this range will be truncated to the appropriate limit.

Table 7 Schedule of ADP-induced platelet aggregation sampling and a maximum acceptable deviation from the scheduled time

Screening	Scheduled Time Relative to Morning Dose		
	Day -2	Day 1	Day 10
Within 3 to 28 days prior to randomization	After arriving at the study center	Pre-dose (within 120 min. before dosing)	Pre-dose (0 hour: within 5 min. before dosing)
		2 hours post dose (± 5 min.)	2 hours post dose (± 5 min.)
		4 hours post dose (± 10 min.)	4 hours post dose (± 10 min.)
		12 hours post dose (± 15 min.)	12 hours post dose (± 15 min.)
		24 hours post dose (± 15 min.)	24 hours post dose (± 15 min.)
		72hours post dose (± 15 min.)	

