4.3.2 Bleeding time assessment

Bleeding time measurements using Simplate[®] R method will be determined at the times indicated in [Table 8](#). If any bleeding time measurement is >60 minutes, the procedure will be stopped and the bleeding time will be recorded as being greater than 60 minutes (>60 mins) on the appropriate CRF. If the pre-dose bleeding time on Day 1 is >9 minutes the subject should not be dosed and will be discontinued from the study.

The assessment at 48-hours post dose measurement on Day 12 will be performed for the subjects whose bleeding time at the 24-hours post dose on Day 11 is longer than 12 minutes.

The methodology is detailed in Appendix D.

Table 8 **Schedule of starting time for bleeding time measurements and a maximum acceptable deviation from the scheduled time**

Visit, Day	Scheduled Time
1 (Screening)	Within 3 to 28 days prior to randomization
2, Day 1	Pre-dose (within 120 min. before dosing) 4 hours post dose (\pm 15 min.) 24 hours post dose (\pm 15 min.)
2, Day 10	Pre-dose (within 120 minutes of dosing) 4 hours post dose (\pm 15 min.)
2, Day 11	24 hours post dose (\pm 15 min.)
(2, Day 12)	48 hours post dose (\pm 15 min.)

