6.2.3.2 Bleeding times

The bleeding time, as measured by the Simplate[®] R technique, will be read directly from the CRF. Bleeding times which are recorded as being greater than 60 minutes in the CRFs will be treated as being exactly 60 minutes in calculating the mean, but all summary statistics associated with that observation will be asterisked and identified with a footnote indicating that the summary statistics are biased.

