Bleeding time data will be summarized and listed using standard descriptive statistics by treatment group and ethnic group. Graphical representations of the data will also be produced.

(d) Optical aggregometry data

Optical aggregometry data will be summarized by treatment group and ethnic group and listed, both as absolute values and as percentage inhibition, calculated from the formula given in section 4.3.1 of this protocol. Graphical representations of the data will also be produced.

(e) Adverse events

Adverse events will be summarized by System Organ Class and Preferred Term, using MedDRA by treatment group and ethnic group. All adverse event data will be listed for all subjects. Separate listings of all serious adverse events, deaths or other significant adverse events will be presented.

(f) Laboratory data

All laboratory safety data, incorporating hematology, clinical chemistry and urinalysis data and haemocult data for Japanese subjects will be listed, with deviations from the normal range explicitly noted on the listings.

Continuous laboratory data will be summarized using standard descriptive statistics. Both absolute values and change from pre-dose baseline will be summarized. In addition, shift plots will be produced for each variable. All summaries will be by treatment group and ethnic group.

Discrete laboratory data will be summarized using standard descriptive statistics. In addition, shift tables showing change from pre-dose baseline will be produced. All summaries will be by treatment group and ethnic group.

(g) 12-lead ECG data

Twelve-lead ECG data will be summarized and listed using standard summary statistics by treatment group and ethnic group. Both absolute values and change from pre-dose baseline will be summarized. In addition, mean plots showing change from within treatment group across time will be produced.

(h) Vital signs

Vital signs data will be summarized and listed using standard summary statistics by treatment group and ethnic group. Both absolute values and change from pre-dose baseline will be summarized. In addition, mean plots showing change within treatment group across time will be produced for absolute values.

(i) Physical examination

Physical examination abnormalities will be listed.

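### Truncating %PAI at 0 without flagging it makes mean inhibition falsely positive and shrinks its SD where true inhibition is near zero

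*Supplement*

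**What the plan says.** **Platelet aggregation.** %PAI is 100 × (PA_BL − PA_T)/PA_BL. In section 6.2.3.1, "PA_{BL} is the response at pre-dose baseline on Day 1". Section 4.3.1 states "Percentage inhibition will be restricted to limits 0 and 100", and section 6.2.3.1 repeats the same limits and adds that "any data falling outside this range will be truncated to the appropriate limit". Neither section asks for truncated values to be marked or counted. Section 6.4(d) then summarizes and lists aggregometry "both as absolute values and as percentage inhibition, calculated from the formula given in section 4.3.1 of this protocol", by treatment group and ethnic group, with graphs. The standard statistics in section 6.4 are mean, SD, median, minimum and maximum.

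**Bleeding time.** Section 4.3.2 ends the measurement at 60 minutes: "the procedure will be stopped and the bleeding time will be recorded as being greater than 60 minutes". Section 6.2.3.2 says such values "will be treated as being exactly 60 minutes in calculating the mean, but all summary statistics associated with that observation will be asterisked", with a footnote saying that the statistics are biased.

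**Status.** Both variables belong to the secondary objectives (section 2.2). One of these is the relation between plasma concentrations and platelet aggregation inhibition. Section 6.4 plans no test or margin for either. The SAP announced in section 6.1 is not among the documents.

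**The concern.** A floor at 0 treats measurement error asymmetrically. If a subject has no real inhibition, the post-dose response lies above the baseline response about as often as below it, so %PAI is negative about half the time. The rule removes every negative error and keeps every positive one.

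The plan contains cells of this kind:

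- **Placebo.** Twelve subjects in all. Section 6.4 pools the two cohorts and summarizes by ethnic group, which leaves 6 per group.
- **Late samples on active drug.** Table 4 schedules aggregometry 72 hours after the last dose, and Table 1 also marks Visit 3. For the single dose, section 3.2 expects plasma drug to be almost gone by 72 hours, on a half-life of 8–12 hours. That is 6 to 9 half-lives. Low inhibition at that point is an inference from plasma levels, not something the protocol states.

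At stake are the placebo reference and the recovery end of the %PAI profile. The low-concentration end of the PK/PD relation is also at stake, if truncated values are used there. The two PD variables are also treated unequally: limited bleeding times are marked as biased, limited %PAI values are not.

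**Working it through.** **The plan's own figure.** None exists for this endpoint. The only powered comparison in section 6.5 concerns pharmacokinetic exposure and does not enter here.

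**Inputs.** From the documents: the formula, the limits 0 and 100, and 6 placebo subjects per ethnic group (12/2). Assumed, because the documents do not give them: the SD of an individual %PAI value, taken as 5 to 20 points; alternatively, a single-response SD of 4 to 10 points around 85% aggregation.

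**Step 1: bias at true zero.** For X ~ N(0, s):

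- E[max(0, X)] = s/√(2π) = 0.399 s
- SD[max(0, X)] = s √(1/2 − 1/(2π)) = 0.584 s

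**Step 2: bias at true inhibition m.** With z = m/s, the bias from the floor is mΦ(z) + sφ(z) − m.

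| SD of %PAI | m = 0 | m = 5 | m = 10 | m = 20 |
|---|---|---|---|---|
| 5 | +2.0 | +0.4 | 0.0 | 0.0 |
| 10 | +4.0 | +2.0 | +0.8 | +0.1 |
| 15 | +6.0 | +3.8 | +2.3 | +0.6 |
| 20 | +8.0 | +5.7 | +4.0 | +1.7 |

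**Step 3: the protocol's ratio.** Simulation at true zero inhibition, with noise in both PA_BL and PA_T, mean 85%:

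| Response SD | Mean %PAI as calculated | Mean truncated | SD as calculated | SD truncated |
|---|---|---|---|---|
| 4 | −0.2 | +2.5 | 6.7 | 3.7 |
| 7 | −0.7 | +4.3 | 11.9 | 6.2 |
| 10 | −1.4 | +6.1 | 17.3 | 8.6 |

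The untruncated ratio has a small negative bias of its own. It is several times smaller than the one the floor introduces.

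**Step 4: a placebo cell of 6.** The truncated mean is above zero unless all six readings are at or below zero: probability 1 − (1/2)^6 = 98%, whatever the SD. The population median does not move, but the median of six truncated values has expectation +1.4, +2.4 and +3.4 points in the three rows of Step 3, against −0.1 to −0.4 untruncated.

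**Step 5: the upper limit.** If PA_T is not negative, %PAI cannot exceed 100, so the cap at 100 does almost nothing.

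**Step 6: bleeding time.** The distribution on drug is not given. Under assumed lognormals, replacing values above 60 by 60 has these effects:

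| Median (min), log SD | Share above 60 | Mean | SD |
|---|---|---|---|
| 10, 0.7 | 0.5% | 12.8 → 12.7 | 10.2 → 9.6 |
| 20, 0.7 | 6% | 25.5 → 24.1 | 20.3 → 15.2 |
| 40, 0.7 | 28% | 51.1 → 40.0 | 40.6 → 17.1 |

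The median is unchanged as long as fewer than half of the values exceed 60.

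**The case against.** The case against acting has real weight.

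- **Absolute aggregation is reported untruncated** (section 6.4(d)). A reader might infer that the rule hides the return to baseline. It does not: placebo drift and recovery remain visible on the absolute scale, and %PAI can be recomputed from the listings. This stands, although the %PAI tables and plots themselves stay biased.
- **The effect is local.** Section 1.1 reports more than 80% inhibition at all multiple doses studied earlier. A few points on the placebo mean are small beside that, and at such inhibition the floor is inert. This stands.
- **Nothing formal depends on it.** PD is secondary, no active–placebo test is planned, and no PK/PD model is specified. Distortion of the PK/PD curve is therefore conditional on truncated values being used there. The SAP may also add detail.
- **The sizes are assumed.** Responses are averaged over duplicate runs (section 4.3.1), which reduces noise, and the upper end of the SD range may be too high. The direction and the 0.40 × SD relation do not depend on this.
- **The median is also planned.** This helps less than it seems with 6 subjects (Step 4).

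A reader might also infer that the bleeding-time rule is an equal fault, so that both PD variables are distorted. The documents do not support that. The measurement stops at 60 minutes, so the true value is never observed. The plan marks the affected statistics as biased and already includes the median. The subject-level and escalation criteria use individual values, not the capped mean. How much the cap moves the mean depends wholly on an assumed distribution and can be almost nothing.

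**Conclusion.** The point holds for %PAI near zero inhibition. Followed as written, the plan reports positive mean inhibition where there is none, with too small an SD and no sign in the tables that values were changed. The bias at true zero is 0.40 × SD, about +2 to +8 points for an assumed SD of 5–20, and the SD falls to about 58% under normal error (50–55% in the ratio simulation). At 20% true inhibition the bias is about 0.1 point for SD 10, although it is still 1.7 points for SD 20. The result assumes roughly symmetric error around zero inhibition; its size rests on an SD that the documents do not give.

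The consequence is limited: a descriptive secondary endpoint, with absolute aggregation available as a check. It is worth correcting because the correction is cheap. For bleeding time, only a small improvement in presentation is warranted.

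**What to change.** 1. In sections 4.3.1 and 6.2.3.1, delete the truncation for summary tables, mean plots and any PK/PD analysis, and use %PAI as calculated.
2. If truncated values are kept for display, flag each one in the listings and give the number truncated per treatment group, ethnic group and time point.
3. Optionally, in section 6.2.3.2, add the number of bleeding times above 60 minutes to each summary and lead with the median in cells that contain such values.

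The cost is wording and programming; no data collection changes. The downside is that some negative individual %PAI values will appear and need a short note that they reflect ordinary variation around baseline.
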